Protocol Title: *The Impact of Meditation on Anxiety and Post-Operative Pain in Pediatric Patients Undergoing Urological Surgery*

Principal Investigator: *[name].*

1. Objectives

Describe the purpose, specific aims, and hypothesis:

1. The aim of this study is to assess anxiety in pediatric patients preoperatively, perioperatively, and postoperatively and whether meditation reduces anxiety in the days before, during, and after the surgery.
2. The second aim of this study is to see if longitudinal meditation is associated with decreased postoperative pain by examining whether the group prescribed meditation has reduced pain medication intake, measured by the frequency of liquid analgesic medicine intake.

4. Number of Subjects/Records/Samples Collected

Indicate the total number of subjects to be accrued/records reviewed/samples collected across all sites: 60, including 30 controls and 30 study subjects.

5. Recruitment Methods

Describe when, where, and how potential subjects will be recruited:

Patients will be identified from the Urology clinic. Pediatric patients between the ages of 6 to 18 who will be undergoing urological surgery will be selected for this study along with their parents. Recruitment will begin in the clinic after surgery is scheduled.

6. Multiple Site N/A

A site is defined as an institution/organization/university that is collaborating with Augusta University

If this research involves multiple sites, specify the lead site and describe the roles of each site in the study.

If Augusta University will serve as the lead site, indicate that all required approvals are already obtained or will be obtained at each site prior to project implementation. In addition:

Describe the processes you have in place to ensure successful coordination of activities among sites. For example, do all sites have the most current version of the protocol, consent document, and HIPAA authorization? How will modifications be communicated to sites and approved prior to implementation? How will participating sites be kept abreast of any problems, interim results, or the eventual closure of the study?

Describe the mechanisms you have in place to ensure that all local site investigators conduct the study appropriately and that engaged participating sites safeguard data as required by local information security policies. Please confirm that all non-compliance and /or unanticipated problems associated with the study protocol or applicable requirements will be reported in accordance with local policy.

Click here to enter text.

7. Reliance Agreements/Single IRB N/A

Reliance agreements (i.e. IRB Authorization Agreement (IAA), Individual Investigator Agreement (IIA), etc.) are formal arrangements between institutions allowing the IRB of one institution to rely on the IRB of another institution for review of human subjects research. Investigators working at multiple institutions, each having an IRB, may choose to have one IRB become the IRB of record over some or all participating sites. This means that the AU IRB is either the reviewing IRB (IRB of Record) or is relying on another IRB for IRB oversight of the research activity.

has eleven questions on a five-point scale ranging from “Not at all” to “A lot”. An example of the meditation video questionnaire is linked here:

https://augusta.qualtrics.com/jfe/form/SV_3DeFFKdJVupMJQq (experimental group)

https://augusta.qualtrics.com/jfe/form/SV_2b2DZ9x16jY9IzQ (PeSSKi questionnaire)

The PeSSKi questionnaire will be in this form on another page for the meditation group. The control group will receive just the PeSSKi questionnaire.

Data will be collected from medical records.

c. Data Types and Source Records:

Briefly describe the actual source records or measures that will be used to collect data about participants. (All surveys, interview scripts, and data collection forms will be attached elsewhere in the application. Do not add other documents to the protocol.) Describe what data will be collected and how it will be collected at all measurement/data collection time-points.

Data will be collected from electronic medical records, and the study questionnaires. Data collected from the EMR will include type of surgery, demographics, prior diagnoses and meditation experience, vital signs, and pain medication usage.

d. Describe the procedures performed to lessen the probability or magnitude of risks:

All data will be managed in a secure format and according to all applicable regulatory guidelines. Subjects will be assigned a study ID number. All medical records information will be entered into the secure database by the PI or designated study team members. A key linking the patient identifiers and the study ID will be stored separately from the data collection form. Only the approved investigator or study team members with username/password access will review medical records and the study information that is collected and stored on the secure drive. The original signed informed consent documents will be secured in a locked cabinet that is accessible only to members of the study team. Surveys will be labeled with a subject ID.

All data will be stored on an AU Secure HUMAN Box folder with access only given to study team members approved by the IRB.

e. Describe the duration of an individual subject’s participation in the study and the time involved also include the overall duration of the project:

Active participation in the study will last for about one month, this includes three weeks pre-operatively and one week post-operatively. Total duration of the project is approximately two years.

v. *How long will the data and/or specimens be stored?*
According to AU and GA BOR policy

vi. *Describe whether, and how, subjects can request withdrawal or destruction of their information or biospecimens.*
 Subject must contact the PI as indicated on the consent form to request withdrawal of their information.

vii. *Who will have access to the data or specimens?*
Only approved study team members

viii. *Who is responsible for receipt or transmission of the data and/or specimens?* N/A
 Click here to enter text.

ix. *How will data and/or specimens be transported?* N/A
 Click here to enter text.

10. Provisions to Monitor the Data to Ensure the Safety of Subjects N/A

The plan might include establishing a data monitoring committee and a plan for reporting data monitoring committee findings to the IRB and the sponsor.

a. *Describe the plan to periodically evaluate the data collected regarding both harms and benefits to determine whether subjects remain safe.*
 Click here to enter text.

b. *Describe what data are reviewed, including safety data, untoward events, and efficacy data.*
 Click here to enter text.

c. *Describe how the safety information will be collected (e.g., with case report forms, at study visits, by telephone calls with participants).*
 Click here to enter text.

d. *Describe the frequency of data collection, including when safety data collection starts.*
 Click here to enter text.

e. *Describe who will review the data.*
 Click here to enter text.

f. *Describe the frequency or periodicity of review of cumulative data.*
 Click here to enter text.

g. *Describe any conditions that trigger an immediate suspension of the research.*
 Click here to enter text.

13. Potential Benefits to Subjects

Describe the potential benefits that individual subjects may experience from taking part in the research.

There is the potential for reduction of anxiety using meditation. No benefits can be guaranteed.

14. Confidentiality

Describe the procedures for maintenance of confidentiality.

Patients will be assigned a study ID for entry into the data collection sheet. A key linking the patient identifiers and the study ID will be stored separately from the data collection form and will be destroyed at the conclusion of the study. Both documents will be stored on the secure drive provided by IT specifically for the study and will be available only to study team members with username/password access. No identifiable participant information will be used in any publication or presentation materials. All study information will be kept confidential per HIPAA regulations. All investigators have undergone proper research training for evaluation and handling of patient information through CITI.

15. Incomplete Disclosure, Authorized Deception, or Deception N/A

See the Deception Policy on Augusta University Website.

If the study will use incomplete disclosure or deception, describe the incomplete disclosure or deception, and provide a rationale explaining why it is necessary to the research.

Click here to enter text.

Describe the debriefing process that will be used to make participants aware of the incomplete disclosure or deception, including their right to withdraw any record of their participation.

Click here to enter text.

experience conducting human subject research. The PI and all study members' education and credentials are listed on their linked CV and CITI training

a. Describe the availability of medical or psychological resources that subjects might need as a result of an anticipated consequences of the human research.

n/a

b. Describe your process to ensure that all persons assisting with the research are adequately informed about the protocol, the research procedures, and their duties and functions.

Each of the research team members, [name], [name], [name], [name], and [name] have been involved in the development of the protocol for "The Impact The Impact of Meditation on Anxiety and Post-Operative Pain in Pediatric Patients Undergoing Urological Surgery". Each member of the research team understand their roles in data collection and interpretation. The research team will meet 1 week prior to data collection for a final review the protocol.

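### Aim 2 counts only liquid analgesic doses, which is narrower than the pain medication intake it stands for and than the medication data the protocol plans to collect

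*Protocol*

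**What the plan says.** Section 1 (Objectives) of the Protocol sets the second aim as finding out whether "longitudinal meditation is associated with decreased postoperative pain". Pain is to be inferred from whether the meditation group shows "reduced pain medication intake, measured by the frequency of liquid analgesic medicine intake".

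Item c (Data Types and Source Records) lists the extraction: "Data collected from the EMR will include type of surgery, demographics, prior diagnoses and meditation experience, vital signs, and pain medication usage". It names no formulation.

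The population in section 5 is "Pediatric patients between the ages of 6 to 18 who will be undergoing urological surgery", and the size in section 4 is "60, including 30 controls and 30 study subjects". Item e describes active participation of about one month: "this includes three weeks pre-operatively and one week post-operatively".

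No visible passage says that all participants receive only liquid analgesics, or makes eligibility depend on formulation.

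**The concern.** Aim 2 moves in two steps from a broad idea to a narrow count: from postoperative pain to pain medication intake, and from intake to how often a liquid analgesic is taken. The second step drops any dose in another form. Such a dose is still pain medication, and a participant who takes it is still treating pain, yet the count does not move.

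Among the source data listed in the visible text there is no pain score, so analgesic intake carries aim 2 alone. If non-liquid doses occur, the count understates intake in the participants who take them. When that happens equally often in both groups, the recorded difference shrinks and, where some participants take no liquid at all, the spread relative to it grows. With 30 per group there is little room for that loss.

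**Working it through.** **The text side by side**

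- Construct (section 1, aim 2): postoperative pain, inferred from pain medication intake.
- Outcome (section 1, aim 2): frequency of liquid analgesic intake.
- Data (item c): pain medication usage, formulation not limited.

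The outcome is a subset of both the construct and the data. Analysing a subset of what is collected is not a contradiction. The subset equals the whole only if every analgesic dose is liquid.

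**Illustration of size, equal use in both groups**

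For aim 2 the visible text gives no mean, SD, effect size, test or power, so there is no stated figure to reproduce. Only n = 30 per group comes from the Protocol (section 4). Assumed: true means m = 8 (control) and 5.6 (meditation) doses, SD s = 4, two-sided 5% t-test, and a non-liquid share of 20%. The noncentrality is difference / (SD × √(2/30)), with 58 degrees of freedom. SD is the square root of the average of the two group variances.

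1. *All doses counted.* Difference 8 − 5.6 = 2.40, SD 4. Noncentrality 2.40 / (4 × 0.2582) = 2.32. Power 63%.

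2. *Mixed use: 20% of each participant's doses are non-liquid* (q = 0.8 counted). Difference 0.8 × 2.40 = 1.92. Variance q²s² + q(1 − q)m: 10.24 + 0.16 × 8 = 11.52 and 10.24 + 0.16 × 5.6 = 11.14, so SD 3.37. Noncentrality 1.92 / (3.37 × 0.2582) = 2.21. Power 58%.

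3. *All-or-none use: 20% of participants take only non-liquid forms and score zero* (p = 0.2). Difference again 1.92. Variance (1 − p)(s² + m²) − ((1 − p)m)²: 0.8 × 80 − 6.4² = 23.04 and 0.8 × 47.36 − 4.48² = 17.82, so SD 4.52. Noncentrality 1.92 / (4.52 × 0.2582) = 1.65. Power 37%.

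Range over the assumed SD, at a 20% share:

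| SD | All doses counted | Mixed use | All-or-none, scored zero |
|---|---|---|---|
| 3 | 86% | 80% | 48% |
| 4 | 63% | 58% | 37% |
| 6 | 33% | 32% | 23% |
| 8 | 21% | 20% | 16% |

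The loss is small when everyone mixes forms and substantial when some participants take no liquid at all. The document does not say which pattern, if either, applies.

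**The case against.** The strongest reply is that the visible text is incomplete. Sections 2, 3 and 8 and the start of the procedures are not shown, and a liquid-only condition, eligibility rules or the method of allocation could stand there. The word liquid may reflect a known local practice. The age range alone does not show that tablets are used; the document says nothing on formulation by age. All of this stands, and it is why the point is conditional.

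It is also fair that broad collection with a narrower outcome is compatible, and that the broader data may allow a later repair. But widening the outcome after the data have been seen would be a post hoc change, so the possibility of repair is a reason to settle it now.

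Three stronger readings are tempting and are not supported.

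- A reader might infer that the comparison is biased towards meditation. That needs a systematic difference in formulation use between the groups. Assuming no true effect, mean 8, SD 4, and 10% of controls against 30% of meditation participants scoring zero, the recorded means would be 0.9 × 8 = 7.2 and 0.7 × 8 = 5.6, with a significant result in 25% of trials. Nothing in the document suggests such a gap, and swapping the shares reverses the direction. The visible text does not state randomisation, but the sections not shown may. Under random allocation, chance imbalance is already within the 5% error rate.
- A reader might fault the Protocol for not saying whether a participant with no liquid doses scores zero or is left out. That is a scoring rule commonly left to the SAP. It enters here only as an assumption of the all-or-none illustration.
- A reader might assume that the medical record captures every dose in the postoperative week. The visible text does not confirm that it covers doses taken at home, whatever their form.

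**Conclusion.** The point holds in a conditional form and should be fixed; confidence is medium. The aim 2 outcome is narrower than the intake it is meant to measure and than the data planned, and it leaves out non-liquid doses unless every participant receives liquid only. If that condition is met, nothing is lost.

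If it is not met and use is equal in both groups, the consequence is mainly reduced power: from 63% to between 58% and 37% in the two patterns illustrated at SD 4. These figures rest on assumed means, SD, test and shares, and they are not a shortfall against any power the Protocol claims. Bias is possible only with a systematic between-group difference in formulation use, for which the document gives no evidence. The actual size cannot be derived from it.

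**What to change.** Before any outcome data are reviewed, reconcile section 1 with item c. Define the aim 2 outcome as the frequency of postoperative analgesic doses in any formulation, taken from the medication data already planned, and report liquid-only intake as a descriptive item. If all participants do receive liquid only, say so and leave the measure as it is.

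The cost is a one-line change to aim 2 and, if the data form does not already have it, a slightly fuller medication entry (dose and form). No further participants are needed. This assumes that the planned sources capture non-liquid doses as well as they capture liquid ones, which should be checked. A dose count in any formulation still does not distinguish drugs or strengths, but that is equally true of the liquid-only count. No view is taken on which analgesic or formulation should be given.

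### Aim 2 infers less postoperative pain from a bare count of liquid analgesic intakes, which follows neither the drug nor the amount taken

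*Protocol*

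**What the plan says.** Section 1 (Objectives), aim 2, asks whether "longitudinal meditation is associated with decreased postoperative pain by examining whether the group prescribed meditation has reduced pain medication intake". The intake is "measured by the frequency of liquid analgesic medicine intake". The unit is thus one intake of a liquid analgesic; no drug, strength, amount or reason for giving enters the measure.

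Item c (Data Types and Source Records) names the medical record as the source for "type of surgery, demographics, prior diagnoses and meditation experience, vital signs, and pain medication usage". The medication entry is not broken down further.

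Three other statements set the setting:
- Section 4 gives the size as "60, including 30 controls and 30 study subjects".
- Section 5 recruits "Pediatric patients between the ages of 6 to 18", with no limit on procedure beyond urological surgery.
- Item e sets participation at "three weeks pre-operatively and one week post-operatively".

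**The concern.** Medication intake is used here as a stand-in for pain, so it should fall when pain falls and rise when pain rises. A plain frequency need not do so. If a child with worse pain is moved to fewer but stronger or larger doses, the count drops and the child appears to have less pain. A child taking small, mild doses more often appears to have more.

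The eligible range of ages and procedures makes differences in drug and in amount per intake likely. If those differences are unrelated to group, they add noise. If they differ between groups, by chance with 30 per group or because treatment changes what is given, they shift the comparison itself. A lower count in the meditation group could then reflect a different pattern of prescribing, and a real reduction in pain could be missed.

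**Working it through.** **Reproducing the plan's figure.** The only design figure is 60 (30 per group). The protocol text at hand gives no significance level, power, effect size or SD with it, so it cannot be reproduced. For scale, at an assumed two-sided 5% and 80% power, the detectable standardised difference is (1.960 + 0.842) × √(2/30) = 0.72 SD.

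**Step 1: ordering (no assumed figures).** Child A takes one intake of amount a. Child B takes two intakes of amount b each, of the same drug.
- Frequency: A = 1, B = 2, so A always ranks as having less pain.
- Amount: A = a, B = 2b, so A has taken more whenever a > 2b.

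The two measures then rank the children in opposite order. With different drugs the count still reads 1 against 2, however much stronger A's drug is.

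**Step 2: scheduled doses (conditional, all inputs assumed).** The protocol does not say whether any dose is given on a schedule. Suppose it is:
- m = 6 as-needed doses per child in the control group;
- a 33% reduction with meditation, so 6 × 0.67 = 4.02;
- variance 1.5 × mean for as-needed doses;
- S scheduled doses per child in both groups;
- 30 per group, two-sided 5%.

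Formulas:
- rate ratio = (4.02 + S) / (6 + S);
- absolute difference = 6 − 4.02 = 1.98, whatever S is;
- SD = √(1.5 × (6 + 4.02)/2 + V), where V is the variance of scheduled doses between children;
- power = Φ(1.98/SD × √(30/2) − 1.960).

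With S = 0: SD = √7.515 = 2.74, standardised difference 0.72, power 80%.

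| S | Rate ratio | Power if S is the same in every child (V = 0) | Power if S varies (V = S) |
|---|---|---|---|
| 0 | 0.67 | 80% | 80% |
| 4 | 8.02/10 = 0.80 | 80% | 62% |
| 8 | 12.02/14 = 0.86 | 80% | 49% |
| 12 | 16.02/18 = 0.89 | 80% | 41% |

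Range: for control means of 4 to 8 as-needed doses, power is 63% to 90% with no scheduled doses and 24% to 59% with 12 that vary between children.

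Scheduled doses therefore always pull the ratio towards 1. They leave the absolute difference alone, and they reduce power only if their number differs between children.

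**The case against.** The strongest reply has five parts.

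1. *Only liquids count.* A reader might infer that every analgesic intake scores one. The text does not support that: a tablet or an injection would not enter the count at all. The ordering problem therefore holds among liquid intakes.

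2. *Scheduled dosing is not mentioned.* A reader might conclude that routine doses do dilute the measure, and picture 4 scheduled plus 2 as-needed doses a day falling from 6 to 5 (1/6 = 17%) while the as-needed part falls from 2 to 1 (50%). Those doses are invented, and the difference is one dose on either scale. A smaller percentage is not in itself a loss of power. Nor do the documents show that only as-needed doses can respond to pain: the measure is intake, and families may skip scheduled doses when a child is comfortable. This objection stands, so dilution is only a conditional point.

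3. *Details may be recorded elsewhere.* The protocol template says collection forms are attached outside it, and an analysis plan may set counting rules. It would therefore be wrong to say that dose is never captured. But the protocol does not merely leave the measure open. It names a frequency, and a later document that replaced it would depart from the stated aim.

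4. *Adjustment is possible.* Type of surgery and demographics are collected, so some variation in prescribing could be adjusted for or stratified. That helps with noise but does not make one large intake and one small intake different.

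5. *An as-needed count also depends on prescribing.* A child covered by scheduled doses may need few others, while a child without them has every dose counted as as-needed. This stands, and is why an as-needed count should not replace the present measure.

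**Conclusion.** The concern holds for the measure as stated. A bare frequency of liquid intakes does not follow drug or amount, and it can rank children in the opposite order from what they took. That conclusion rests on the wording of aim 2 alone.

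Its effect on the group comparison cannot be sized from the protocol. It depends on how far drug and amount per intake vary, and on whether they vary by group. The further loss from scheduled doses is conditional on such doses being given, and the power loss also on their varying between children; the 62% to 41% rests on assumed inputs. The documents do not support saying that the count mainly reflects prescribing, only that it may do so in part.

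The point is worth acting on before data collection. It bears on the pain conclusion of the second aim and does not prevent the study from running.

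**What to change.** In aim 2, keep the frequency and add the total amount of each analgesic, in mg/kg, over the postoperative week. Report opioid and non-opioid separately, since amounts of different drugs should not be summed. State that the pain conclusion rests on frequency and amount together: a fall in one with a rise in the other would not be read as less pain.

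In item c, state that drug, amount, time, weight and order type (scheduled or as-needed) are abstracted from the medical record for each dose. An as-needed-only count can then be a sensitivity analysis. If no dose is scheduled, it equals the main count and nothing is lost.

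The change is to outcome wording and abstraction columns only; no treatment or clinical rule is touched. It costs modest extra abstraction time and more than one measure to report for a second aim in 60 children, some of which may be sparse. The amounts can be totalled only for doses that the record captures.
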